7. STUDY-WIDE NUMBER OF SUBJECTS*

NA

8. STUDY-WIDE RECRUITMENT METHODS*

NA

9. STUDY TIMELINES*

An individual's participation in the study will be one-time for 20 minutes. We expect to complete the study within six months of enrolling the first participant.

10. STUDY ENDPOINTS*

The primary outcome measures include self-reported measures of message acceptance and harm perceptions. Secondary outcome measures include reactance, message liking, source trust, attitudes, and behavioral intentions.

11. PROCEDURES INVOLVED*

Non-vaper participants (regardless of their susceptibility) will first complete the online consent (i.e., STUDY00001220-Screener Consent_Fact Sheet_04.06.24.docx) and screener survey on

INVESTIGATOR STUDY PLAN - REQUIRED

Qualtrics to determine their eligibility for susceptibility and will receive \$1.00 via Prolific for participating in a 5-minute study. We will use the list of eligible participants from the screener survey, who will have been identified as susceptible, to participate in the 20-minute study, as described below.

Eligible participants will complete an online consent (STUDY00001220-Consent_Fact Sheet.v3.013124.docx) and tobacco use questions on a Qualtrics survey before random assignment to one of four experimental conditions in a 2 (Source: expert and peer) X 2 (Presentation: one-sided and two-sided) design. First, participants will view the source description within their assigned condition and view 18 random-ordered messages. See Appendix A. Copies of the messages. They will rate each message for perceived message effectiveness (PME),⁴⁵ a widely used measure of message acceptance by the FDA's tobacco health communication campaigns.^{46,47} They will also rate e-cigarette harm perceptions,⁴⁸ psychological reactance (resistance to the message),⁴⁹ message liking,^{50,51} and source trust.⁵² The process will repeat 18 times, once for each message. Afterwards, participants will complete posttest survey questions about their demographics, attitudes about vaping,⁴⁶ and behavioral intentions to vape.⁵³ We will check manipulation of the source manipulation by asking participants to indicate the source of the message they saw after the first three messages. After completing the study, they will receive \$4.00 via Prolific per its policies for participating in a 20-minute survey. At the end of the study, participants will be extensively debriefed about the hypothetical nature of the message source and the health harm of using any tobacco products, provided with an information sheet about the health effects of e-cigarettes and resources for the Quitlines across the U.S. See Appendix B-1 and B-2 for information about nicotine health harms and resources to quit. They will also complete a questionnaire assessing their understanding of the information regarding quitting resources. At the end of the survey, each participant is given a unique code to input into Prolific to receive compensation. We will double-check responses on our end of the survey and approve them to compensate participants.

12. DATA AND SPECIMEN BANKING*

We will not collect any information directly linked to the identity of individual subjects. It is possible that IP addresses may be collected. We will de-identify the dataset by removing IP addresses. The data will be stored in UMass Chan Medical School OneDrive indefinitely and will be accessible to the PI and the research coordinator. De-identified dataset will be available to other researchers upon request.

13. Data Analysis and Management*

Scores for each measure will be summed and averaged across all messages for each vaping status population. A multi-attribute decision-making MADM framework⁵⁴ will be used to produce a dataset containing data on participant response to each message with source + presentation type. Crowdsourced data will be merged with the Study part 2 data (psychophysiological testing) to rank messages and determine optimal message type.

Once the crowdsourced and psychophysiological data collection is complete, we will use the MADM framework⁵⁴ to determine the optimal combination of message source and presentation type. We will create a decision matrix in which each row represents a message type (source + presentation) and each column (attribute) represents a construct via the crowdsourced and

INVESTIGATOR STUDY PLAN - REQUIRED

psychophysiological studies. Each message type will receive an average score for each self-report (e.g., message acceptance, harm perceptions) and psychophysiological measure (e.g., heart rate, skin conductance, eye-tracking) for each vaping status. The overall rank for each message type will be calculated by taking the average of ranking scores of the crowdsourced and psychophysiological data across the measures within each message type. Each measure will be equally weighted, as a previous study using MADM has indicated no differences in ranks when weighting psychophysiological or self-report measures differently.⁵⁴ We will use statistical software (e.g., Stata, SPSS, R) to conduct analysis.

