4. OBJECTIVES*

The goal of the study is to conduct a crowdsourced testing to examine the effects of source and presentation of e-cigarette educational messages among young adults who currently vape and do not vape but are susceptible. The objectives are to examine young adults' self-reported responses toward message source (expert vs. peer), message sidedness (one-sided vs. two-sided), and messages combining both (source x message sidedness) about anti-e-cigarette messages.

Aim 1: To determine the optimal message source and presentation type for young adult vapers and susceptible non-vapers to increase acceptance of e-cigarette education messages and e-cigarette harm perceptions.

H1. Vapers will report greater message acceptance and harm perceptions than peer and two-sided messages.

Aim 1: Which message source and sidedness strategy is effective for susceptible non-vapers?

INVESTIGATOR STUDY PLAN - REQUIRED

H1. Susceptible non-vapers will report greater message acceptance and harm perceptions to expert and one-sided messages.

Please note that all procedures will be conducted online and there will be no direct in-person interaction between researchers and participants.

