5. BACKGROUND*

Young adults (18-24-year-olds) in the U.S. have the highest rates of e-cigarette use (vaping),¹ with 16-19% of this population identifying as current users, 44-48% ever users, and 11-16% susceptible never users.² Vaping can lead to nicotine addiction and initiation of cigarette smoking³⁻⁷ and is associated with cognitive and affective disorders among young adults.⁸ The U.S. Food and Drug Administration (FDA) has prioritized educating about the health harm of vaping among young adults. However, young adults may avoid^{9,10} or reject¹¹ the current education messages, especially if they currently vape¹²⁻¹⁴ or perceive the messages as “controlling.”¹⁵ It is urgently needed to increase acceptance of e-cigarette education messages¹⁶ to influence their e-cigarette harm perceptions and vaping behaviors.¹⁷⁻²⁰

Using a trusted source²¹⁻²⁴ and presenting messages appropriately^{25,26} can increase message acceptance. According to persuasion theories, one’s tobacco use status may influence individuals’ response to a source and presentation of messages because vapers and susceptible non-vapers differ in their attitudes and personal relevance regarding tobacco use.^{25,27-29} Unfortunately, no research has yet examined the impact of a message source^{22,30} and presentation^{25,31,32} on young adults’ responses to e-cigarette education messages based on their vaping status. Evidence from research with cigarette smokers suggests that vapers will respond defensively to e-cigarette education messages, but susceptible non-vapers will not.^{12,33} Vapers may trust a tobacco health information source with similar attributes (e.g., peer young adults)^{29,34} and accept messages with balanced perspectives that both present negative health effects of vaping and acknowledge their potential reasons for vaping (two-sided; e.g., “vaping can be appealing if others are using it, but it can harm your health”).^{25,31,35} On the other hand, susceptible non-vapers may trust a source with credentials (e.g., scientists)³⁶⁻³⁸ and accept information-only messages (one-sided; e.g., “vaping can harm your health”).^{13,35} Thus, it is critical to understand and use a trusted source and present messages that are appropriate for vapers and susceptible non-vapers to optimize vaping cessation and prevention efforts, making it an important area of study to improve current messaging.

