## Crowdsourcing Study

**Study Design and Power Analysis:** The focus of this proposal is to assess which communication principles influence self-reported responses on source trust, psychological reactance, message liking, attitudes, and behavioral intentions of young adults. Eligible participants will complete an online consent and tobacco use questions on a Qualtrics survey before random assignment to one of four experimental conditions in a 2 (Source: expert and peer) X 2 (Presentation: one-sided and two-sided) design. For the crowdsourcing study of Aim 1, we wish to identify top-rated features to be tested further using psychophysiological testing. We investigated the stability of ranks as a function of number of participants, using simulated data (500 sets of simulated data per run) based on observed outcome distributions from Stevens et al. (2021). These runs indicated that ranks for the top 3 features are stable with 50 participants each receiving 18 messages. Separately for vapers and susceptible non-vapers, within each of 8 possible conditions (2 expert types x 2 peer types x 2 presentation types) we will recruit n=50 participants, or n=400 for each vaping status and n=800 total. Scores for each measure will be summed and averaged across all messages within each vaping status condition. I will use a multi-attribute decision-making (MADM) framework to produce a dataset containing data on participant response to each message with source + presentation type. I will merge crowdsourced and psychophysiological data to rank messages and determine optimal content.

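### Vapers and susceptible non-vapers are ranked separately with no contrast between them, so the plan cannot support a claim that the best message type depends on vaping status

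*Protocol*

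**What the plan says.** Protocol section 13 sets the averaging rule: "Scores for each measure will be summed and averaged across all messages for each vaping status population". The SAP repeats it: "Scores for each measure will be summed and averaged across all messages within each vaping status condition". In the decision matrix each message type gets one average per self-report measure and per psychophysiological "measure (e.g., heart rate, skin conductance, eye-tracking) for each vaping status". Selection is by average rank with equal weights: "The overall rank for each message type will be calculated by taking the average of ranking scores of the crowdsourced and psychophysiological data". The SAP sizes the study in the same stratified way: "Separately for vapers and susceptible non-vapers, within each of 8 possible conditions", 50 participants are recruited, giving 400 per vaping status and 800 in total.

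Neither document gives a between-group contrast, an interaction term, an interval, a significance level or a measure of rank uncertainty. The only other sentence in section 13 on how the analysis is done names software.

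The rationale, however, concerns differences by vaping status. Protocol section 5 says that "no research has yet examined the impact of a message source" and presentation on young adults' responses according to whether they vape. It expects vapers to favour peer sources and two-sided messages, and susceptible non-vapers to favour expert sources and one-sided messages. Section 4 carries this into two hypotheses. The one for non-vapers is clear: "Susceptible non-vapers will report greater message acceptance and harm perceptions to expert and one-sided messages". The one for vapers has lost its comparator: "Vapers will report greater message acceptance and harm perceptions than peer and two-sided messages".

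**The concern.** The background and the paired hypotheses describe effect modification: the effect of source, and of presentation, is expected to change direction with vaping status. The analysis produces two rankings that never meet. A ranking has no outcome that means no difference between groups. It returns a top type in each group whatever the data, and two independent rankings can name different top types even when both groups respond identically. Within-group intervals would not cure this, because a difference between groups has to be estimated as a difference.

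At stake is any statement that messages should be tailored to vaping status. Without a planned contrast it would rest on two winners that happen to differ. A contrast added after the rankings are seen would be post hoc.

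**Working it through.** **The plan's own figure.** 8 cells × 50 participants × 2 vaping-status groups = 800, as the SAP states. The SAP's claim that the ranks of the top 3 features are stable with 50 participants cannot be reproduced, because no means, SDs or stability criterion are given. It also does not address agreement of winners between groups.

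**Number of types ranked.** Protocol section 11 describes four conditions, which gives 400/4 = 100 participants per type in each group. The SAP describes eight cells of 50. Both are carried through.

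**Chance of different winners if all types are equal.** With K types, each is equally likely to be top in each group, so P(different) = 1 − 1/K. K = 4: 1 − 1/4 = 75%. K = 8: 1 − 1/8 = 87.5%.

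**Chance of different winners if the same type is best in both groups.** Simulation, 100,000 runs, with identical true means in the two groups, so every disagreement is chance. Effects are in SDs of participant-level mean scores and are assumed, because the documents give none. The winner is chosen on one measure, or on the mean rank over 7 measures (the two primary and five secondary outcomes in Protocol section 10), with an assumed correlation of 0.5.

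| Shared advantage | 4 types, n=100, one measure | 4 types, n=100, seven measures | 8 cells, n=50, one measure | 8 cells, n=50, seven measures |
|---|---|---|---|---|
| 0 | 75% | 75% | 87.5% | 87.5% |
| 0.1 SD | 63% | 55% | 84% | 81% |
| 0.2 SD | 31% | 16% | 69% | 55% |
| 0.3 SD | 8% | 2% | 44% | 22% |

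Disagreement drops below 50% at a shared advantage between 0.10 and 0.15 SD with 4 types. With 8 cells it does so between 0.20 and 0.25 SD (seven measures) or between 0.25 and 0.30 SD (one measure).

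**What the missing contrast could detect.** Source × status compares four means of 800/4 = 200 participants each. As a difference of differences, SE = √(4 × 1/200) = √0.02 = 0.141 SD. Presentation × status has the same SE. At two-sided 5% (assumed) the interaction detectable with 80% power is (1.96 + 0.84) × 0.141 = 0.40 SD. Power, from Φ(d/0.141 − 1.96):

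- 0.2 SD: 29%
- 0.3 SD: 56%
- 0.4 SD: 81%

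A full crossover of +0.2 SD in one group and −0.2 SD in the other is an interaction of 0.4 SD. For comparison, a source effect within one group has SE √(2/200) = 0.10 SD and a detectable size of 2.80 × 0.10 = 0.28 SD.

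**The case against.** The strongest reply is that Aim 1 asks within-group questions: which type is best for vapers, and which for susceptible non-vapers. Each hypothesis can be examined inside one group, and choosing a best type per group needs no between-group test. That stands, and the group rankings should remain. It does not cover a statement that the groups differ, which section 5 gives as the reason for the study.

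A reader might infer that different winners will usually arise by chance. The documents do not support that, because they give no effect sizes. It is true if the types are equal or nearly so. With 4 types and a shared advantage of 0.3 SD, disagreement occurs in only 2–8% of studies.

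A reader might also infer that the sponsor will treat different winners as proof that tailoring is needed. No passage states such a rule. The opposed hypotheses and the rationale make that reading likely, but it remains an inference.

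The chance figures cover any pair of different winners, not the hypothesised pair. If all 4 types are equal, peer/two-sided on top in vapers together with expert/one-sided on top in non-vapers arises in 1/4 × 1/4 = 1/16 = 6.25% of studies. A wrong pick also costs nothing when the types are equal, and little when they are nearly equal. Both points stand. They limit the harm from the choice of message, but they do not make a claimed group difference sound.

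Finally, the interaction test is weak below 0.4 SD. That is a reason to report estimates with intervals. It is also a reason not to read a non-significant interaction as sameness.

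**Conclusion.** The concern holds in this form: both documents rank within vaping status, neither plans a contrast between the groups, and the plan as written therefore cannot support a claim that the best source or presentation depends on vaping status. Different winners alone are weak evidence. They arise by chance in 75% (4 types) or 87.5% (8 cells) of studies if types do not differ. With a shared best type the range is wide, from 55–63% at 0.1 SD down to 2–8% at 0.3 SD with 4 types, and from 81–84% down to 22–44% with 8 cells.

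The equal-types figures are exact. The others rest on assumed effect sizes, an assumed correlation of 0.5 and self-report data only. The psychophysiological data from Part 2 also enter the final ranks, but their sample size is not in these documents. The within-group selection itself is not at fault. This should be changed before the data are analysed.

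**What to change.** Add to Protocol section 13 and to the SAP:

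- For each primary outcome (message acceptance and harm perceptions), one prespecified model on all 800 participants with source, presentation, vaping status and all their interactions. Source × presentation and the three-way term belong in it because the plan ranks combinations. Report source × status (averaged over presentation) and presentation × status (averaged over source) with 95% intervals.
- A statement that different winners alone do not show that the groups differ, and that any claim for tailoring by vaping status rests on these contrasts.
- The group-specific rankings kept as the Aim 1 output. Do not switch to a pooled ranking because an interaction is not significant: with 29% power at 0.2 SD and 56% at 0.3 SD, that would treat absence of evidence as evidence of sameness.
- A statement that 800 participants give 80% power only for interactions of about 0.40 SD (SE 0.141 SD, two-sided 5%).

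In Protocol section 4, restate the vaper hypothesis with its comparator, so that it predicts higher scores for peer than expert sources and for two-sided than one-sided messages, as section 5 implies. Reconcile the four conditions in Protocol section 11 with the eight in the SAP, so that the number of types ranked is fixed.

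The cost is one extra model per primary outcome and some wording, with no new participants or data. The downside is that a tailoring claim may prove unsupported.

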The proposed research is guided by biobehavioral theories of tobacco regulatory science,^{39,40} psychology,^{15,41} and communication.^{42,43} By using previously tested education messages,⁴⁴ we will determine an optimal combination of message source and presentation type to increase message acceptance and e-cigarette harm perceptions. We will compare the effects of two sources (expert and peer) and two message presentation types (one-sided and two-sided) for young adult vapers and susceptible non-vapers. We will use crowdsourcing (N=800) for post-test self-report measures (message acceptance, harm perceptions) to determine optimal messaging. The goal of this study is to determine optimal message source and presentation for young adult vapers and susceptible non-vapers to increase message acceptance and harm perceptions using crowdsourcing.

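### The only rule for naming the optimal message type gives the two primary outcomes no priority, and no stated analysis tests H1 on them

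*Protocol*

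**What the plan says.** Protocol section 10 sets the hierarchy: "The primary outcome measures include self-reported measures of message acceptance and harm perceptions". It then adds: "Secondary outcome measures include reactance, message liking, source trust, attitudes, and behavioral intentions". Section 11 identifies PME as the measure of message acceptance.

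Protocol section 4 words Aim 1 and both H1 statements in terms of the same two primaries. For one group: "Susceptible non-vapers will report greater message acceptance and harm perceptions to expert and one-sided messages". Section 5 ties them to the decision: "We will use crowdsourcing (N=800) for post-test self-report measures (message acceptance, harm perceptions) to determine optimal messaging".

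Protocol section 13 gives the rule that would actually be run. First, "Crowdsourced data will be merged with the Study part 2 data (psychophysiological testing) to rank messages and determine optimal message type". In the decision matrix, "Each message type will receive an average score for each self-report (e.g., message acceptance, harm perceptions) and psychophysiological measure", separately by vaping status. Heart rate, skin conductance and eye-tracking are given as examples of the psychophysiological measures. Then "The overall rank for each message type will be calculated by taking the average of ranking scores of the crowdsourced and psychophysiological data". On weights: "Each measure will be equally weighted, as a previous study using MADM has indicated no differences in ranks"; the comparison behind that reason is between self-report and psychophysiological weighting.

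The SAP's focus sentence lists exactly the five outcomes that Protocol section 10 calls secondary, and neither primary. It later says that every measure will be scored and averaged over messages. It describes the crowdsourcing part of Aim 1 as a way to pick the best-rated features for psychophysiological work, without naming the measure that rates them.

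**The concern.** Section 5 and section 13 define the optimum differently. Section 5 uses two self-reported outcomes from crowdsourcing. Section 13 uses an equal-weight mean rank over self-report and Part 2 measures, in which the primaries appear only as examples. Neither document states a contrast, model, interval or test for H1.

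Followed as written, the plan can name as optimal a type that is best on neither primary outcome, and nothing requires that disagreement to be shown. The reason given for equal weights does not help, because it addresses self-report against psychophysiology, not primary against secondary.

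H1 has a further difficulty. The vaper version in section 4 compares what vapers report with a kind of message, so its contrast is undefined. The rationale in section 5 suggests that peer and two-sided messages were meant to be favoured in this group, but H1 does not say so.

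**Working it through.** **The plan's own figure.** The SAP gives 8 conditions (four source descriptions by two presentations) with 50 participants each: 8 × 50 = 400 per vaping status, and 400 × 2 = 800. This reproduces. The 50 itself cannot be reproduced, because it comes from simulations on data that are not in the documents. It rests on rank stability; no effect size, power or error rate is stated.

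**Passages side by side.**

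| Place | Outcomes that define the answer | Data source |
|---|---|---|
| Protocol 4 (Aim 1, H1) | PME, harm perceptions | Self-report |
| Protocol 5 | PME, harm perceptions | Crowdsourcing |
| Protocol 10 | PME and harm perceptions primary; five others secondary | Self-report |
| Protocol 13 | Self-report and psychophysiological measures, equal weight | Parts 1 and 2 merged |
| SAP, focus sentence | The five secondary outcomes only | Self-report |

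**Break-even.** Let type A rank 1st and type B rank 2nd on both primaries, with no ties. Let S be a type's rank sum over all other columns.

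- A's total = 1 + 1 + S_A
- B's total = 2 + 2 + S_B
- B is ahead when S_A − S_B > 2, that is, by at least 3 whole places. A net lead of exactly 2 gives a tie.

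This holds for any number of columns.

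**Example with the five measures named in section 13** (PME, harm perceptions, heart rate, skin conductance, eye-tracking):

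| Type | PME | Harm | HR | SC | Eye | Mean rank |
|---|---|---|---|---|---|---|
| A | 1 | 1 | 2 | 2 | 2 | 8/5 = 1.6 |
| B | 2 | 2 | 1 | 1 | 1 | 7/5 = 1.4 |
| C | 3 | 3 | 3 | 3 | 3 | 3.0 |
| D | 4 | 4 | 4 | 4 | 4 | 4.0 |

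B is named optimal. One place on each of three Part 2 columns overrules both Part 1 primaries.

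**Larger matrices (illustration only, because the list of columns is open).** With the five named columns the primaries carry 2/5 = 40% of the weight. If all seven self-report outcomes and the three psychophysiological examples were columns, they would carry 2/10 = 20%. In that case, if B is one place ahead on six of the other eight columns and one behind on two, A scores (2×1 + 6×2 + 2×1)/10 = 1.6 and B scores (2×2 + 6×1 + 2×2)/10 = 1.4.

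**Frequency under assumed correlations.** In 20,000 simulated sets with four types, ten measures and an assumed common correlation between measures, a type first on both primaries failed to finish top or joint top in 40%, 22% and 12% of the sets that had such a type, at correlations 0, 0.3 and 0.6. With seven measures the figures were 31%, 16% and 9%. These depend wholly on the assumptions. They show only that conflict becomes rarer as the measures move together.

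**Precision of a direct comparison on one primary, per vaping status.** Assume complete data, equal allocation, and the SD of participant means as the unit.

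- Two message types: 400/4 = 100 each; half-width 1.96 × √(2/100) = 0.28 SD.
- Source or sidedness main effect: 200 against 200; half-width 1.96 × √(2/200) = 0.20 SD.

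**The case against.** A reader might infer that nothing in the documents links the primary outcomes to the choice of message. That goes too far: section 5 makes the link in so many words. What is missing is an analysis that acts on it.

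A reader might also infer that the composite is illegitimate, or that Aim 1 must be answered from Part 1 alone. The documents do not support this either. The SAP treats crowdsourcing as one component of Aim 1 that feeds psychophysiological testing, and section 13 combines the two. A multi-criterion ranking is a reasonable final step, and section 5 can be read as describing its first stage.

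Three further points carry weight:

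- The primaries are scored. Section 13 gives each type an average on each of them by vaping status, so the descriptive figures that H1 needs exist inside the matrix, and the SAP's later reference to every measure takes them in. But no sentence makes those figures the answer to H1 or requires them to be reported.
- Dilution by the secondary outcomes is inferred. The only self-report columns that section 13 names are the two primaries. The 20% weight is therefore an illustration and not a property of the plan. The five-column example does not need it.
- The reversal is general algebra: any mean rank can disagree with two of its columns. This is true, and it is why the disagreement should be reported and the composite need not be dropped.

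**Conclusion.** The concern holds as a conflict between Protocol sections 5 and 13, with no stated analysis that carries out section 5 or tests H1, and with a SAP focus sentence that omits both primaries. Under the section 13 rule, a net lead of three rank places on the remaining columns is enough to displace a type that is first on both primaries over one that is second on both. With the five named measures, the three Part 2 columns can do this alone (1.6 against 1.4). The break-even assumes untied ranks. The size in this trial is unknown, since the documents give neither the full list of columns nor the correlations between measures, and reversal would be rare if the other measures track the primaries. Severity is modest and confidence medium: the data needed are already collected, but the plan does not say which result answers the hypothesis.

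**What to change.** 1. Correct the SAP focus sentence so that PME and harm perceptions are named as primary and the other five outcomes as secondary, in line with Protocol section 10.
2. State that H1 and the crowdsourcing component of Aim 1 are answered by comparing the four source-by-sidedness types on PME and on harm perceptions separately, within each vaping status. Use a linear model with source, sidedness and their interaction on each participant's mean over the 18 messages, and report differences with 95% confidence intervals. Reword the vaper H1 in Protocol section 4 so that its contrast is defined. If the two primaries favour different types, report both and call neither type best on the primaries.
3. Keep the equal-weight composite with Part 2 as a separate multi-criterion ranking, and report any disagreement with the primary-outcome results.

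The cost is wording in both documents and one extra table per vaping status, from scores the plan already produces. No new participants or data are needed. The downside is that the two primaries, or the two rankings, may disagree and need explaining, and the crowdsourcing part may then end without a single best type.

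### The optimal message type is read off average ranks with no measure of sampling error, so a chance ordering is reported in the same way as a real effect

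*Protocol*

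**What the plan says.** Protocol section 13 (Data Analysis and Management) builds a decision matrix in which "each row represents a message type (source + presentation") and each column is a construct measured in the crowdsourced study or in Part 2. Each type receives a mean score per measure, separately for vapers and susceptible non-vapers. Types are then ranked: "The overall rank for each message type will be calculated by taking the average of ranking scores of the crowdsourced and psychophysiological data". On weights: "Each measure will be equally weighted". The stated use of the result is "to determine the optimal combination of message source and presentation type", and the merged data serve "to rank messages and determine optimal message type". Beyond this, section 13 names only the software.

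Protocol section 4 gives Aim 1 as finding the best source and presentation type for each vaping status. Its directional hypotheses have no analysis attached to them.

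The SAP sets the sample size by rank stability, using 500 simulated datasets per run drawn from the outcome distributions of an earlier study: "These runs indicated that ranks for the top 3 features are stable with 50 participants each receiving 18 messages". It reports no run in which the types do not differ.

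**The concern.** The rule turns means into ranks and ranks into a winner. Ranking discards both the size of the differences and their precision: a gap of a hundredth of a standard deviation and a gap of half a standard deviation give the same order. Nothing later in the plan restores that information.

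The product of Aim 1 is a statement that a given type is optimal for vapers, or for susceptible non-vapers. As written, the rank table cannot tell a reader whether that statement rests on evidence or on chance. Chance patterns can also look persuasive. All self-report measures come from the same respondents, so a type that happens to draw more favourable respondents will tend to lead on several measures at once, and agreement across measures is easily taken for confirmation.

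The stability statement in the SAP does not answer this. It was obtained under whatever differences the earlier study's distributions contained, and the documents do not show those distributions.

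**Working it through.** **Inputs from the documents**
- Eight cells of 50 per vaping status (SAP): 50 × 8 = 400 per status, and 400 × 2 = 800 in total. This reproduces the plan's sample size. The rank-stability result itself cannot be reproduced, because its source distributions are not given.
- Four message types. Protocol section 13 defines matrix rows as source plus presentation, and section 11 has "random assignment to one of four experimental conditions in a 2 (Source: expert and peer) X 2 (Presentation: one-sided and two-sided) design". That gives 400 / 4 = 100 per type per status. Eight cells of 50 were run as the alternative.
- Seven self-report measures: two primary and five secondary (protocol section 10).

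**Assumptions, because the documents give no figures**
- Normally distributed mean scores, with correlation between measures of 0, 0.3, 0.5 or 0.7.
- Part 2 is left out except where stated; its size and design are unknown.

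**Step 1: the rule as a formula.** For type t and K measures, average rank(t) = (1/K) × the sum over k of the rank of type t's mean on measure k. The type with the best average rank is first. A finite set of numbers always has a minimum, so a first place, sole or tied, exists in every dataset. This needs no simulation.

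**Step 2: no true effect.** 40,000 simulated trials per setting (60,000 for the last row):

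| Correlation | 0 | 0.3 | 0.5 | 0.7 |
|---|---|---|---|---|
| Sole first, four types of 100 | 0.859 | 0.914 | 0.935 | 0.956 |
| Sole first, eight cells of 50 | 0.895 | 0.934 | 0.944 | 0.953 |
| One type first on all seven measures, four types | 0.0002 | 0.020 | 0.077 | 0.198 |

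Repeat runs agree to within about a percentage point, hence about 85–96% for a sole winner with four types; the remainder are ties. The median gap between best and worst average rank runs from 1.0 (correlation 0) to 2.3 (correlation 0.7) on a scale from 1 to 4. Adding three psychophysiological measures with an assumed 25 participants per type leaves the sole-winner rate at 0.88–0.94.

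By symmetry, any type named in advance comes first in about 25% of null trials with four types. The chance that the hypothesised type comes first in at least one vaping status is 1 − 0.75² = 43.75%, and in both it is 0.25² = 6.25%.

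**Step 3: would resampling reveal this?** Resample participants within type, repeat the ranking, and record how often each type is first (its rank-1 share). In null trials with four types, the winner's median share is about 0.51–0.56. It reaches 0.90 in only 0.8–3.4% of null trials. A reader shown the share would see that the lead is weak.

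**Step 4: a real effect.** One type is better by 0.2 SD on all seven measures. The table gives the chance that the right type is named alone, over correlations from 0.7 to 0:

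| | Rule as planned | Named only if share is at least 90% |
|---|---|---|
| Four types of 100 | about 87–100% | 31–93% |
| Eight cells of 50 | about 57–95% | about 4–43% |

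With four types at 0.3 SD the figures are 98–100% and 69–100%. At 0.5 SD the gated rule names the right type in at least 98.9% of trials.

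**The case against.** The best defence is that this is selection, not testing. Any ranking has a top, the SAP speaks of finding features to carry into psychophysiological testing, and choosing among truly equal options loses little. Step 4 supports this: when one type is better, the planned rule usually finds it. That part stands. It is why the leading type should still be named, and why a hard threshold is not needed. The defence does not cover the final use, though. Section 13 applies the ranking after both data collections are complete and treats the result as the determination of the optimal type, with nothing after it.

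A second defence is that part of the method lies outside these documents. The ranking framework is cited rather than described, and Part 2 has its own design. A reporting convention there cannot be ruled out, but neither document states one. Nor does anything forbid showing spread beside the mean scores; the plan simply does not provide for it.

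A third is that the larger gap is the absence of any analysis of the section 4 hypotheses. Contrasts with intervals would indeed warn a reader. They would not attach uncertainty to the ranking, which combines all measures and produces the headline.

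A reader might infer a stronger claim: that the plan has a 100% false-positive rate. The documents do not support that reading. That something always comes first is true of any ranking, the plan promises no error rate, and in about 4–14% of null trials with four types the outcome is a tie, which names no single optimum.

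**Conclusion.** The point holds in a limited form. Within each vaping status the optimal type is determined from average ranks alone, and the plan has no means of showing whether the order exceeds chance. With four types of 100 and seven self-report measures, no true effect still yields a sole winner in about 85–96% of trials and a clean sweep of all seven measures in about 0–20%.

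That a first place always exists follows from the rule itself. The percentages rest on the assumed correlations and on self-report measures only; the size and design of Part 2 are not in the documents. The conclusion is the same for four types or eight cells.

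It does not follow that the rule picks poorly when types differ, or that naming a leader should be barred below some threshold. This is a cheap improvement to reporting, not a flaw in the design.

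**What to change.** Add to protocol section 13 and to the SAP:

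- Within each vaping status, participants will be resampled with replacement within condition (at least 2,000 bootstrap samples). Part 2 participants will be resampled according to the Part 2 design.
- The full ranking will be repeated in each sample. Each type's rank-1 share and a rank interval will be reported beside its overall rank.
- The top-ranked type will be named as the leading type. The conclusion will state its rank-1 share, list the types that together hold 90% of first ranks, and say that the data do not distinguish a single optimum when that list has more than one type.

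The wording should also say how ties for first are counted and whether the rows are the four types or the eight cells. A rule that withholds the name of a leading type below a fixed share is optional. Its price is shown in Step 4 and is steep with eight cells.

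Cost: a few lines of text, a short script on data already being collected, and no extra participants. The drawback is that the conclusion may be less definite, most often when true differences are small.
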